#### **Waiving Informed Consent**

- **16.** In general, IRB may waive or alter the requirement of informed consent under 45 CFR 46.116(f) (3), provided that the IRB finds documents that all of the following four conditions are met:
  - 1. (i) The research involves no more than minimal risk to subjects;
  - **2.** (ii) The research could not practicably be carried out without the requested waiver or alteration;
  - **3.** (iii) If the research involves using identifiable private information or identifiable biospecimens, the research could not practicably be carried out without using such information or biospecimens in an identifiable format;
  - **4.** (iv) The waiver or alteration will not adversely affect the rights and welfare of the subjects; and
  - **5.** (v) Whenever appropriate, the subjects or legally authorized representatives will be provided with additional pertinent information after participation.
- 17. \* 6.9 Are you seeking an HSPC approval to waive consent entirely for this population? Yes No

#### **Waiving Elements of Informed Consent**

\* 6.10 Are you seeking an HSPC approval to waive or alter any of the required elements of informed consent for this study population? The list of elements normally included in an informed consent are shown below.

Yes No

- That the project is a research study
- Purpose of the research

- That participation is voluntary and can be discontinued at any time without penalty
- Clear description of procedures and their duration. Note procedures that are experimental (i.e., newly developed or of unknown benefit or risk), if any
- Risks from participation, if any
- Benefits to the individual from participation, if any
- A statement describing the extent to which confidentiality of records identifying the subject will be maintained, if at all
- o Point of contact for questions or problems regarding the study
- Point of contact for HSPC
- o Signature of participant and/or legally authorized representative

#### **Future Contact After Research Ends**

18. \* 6.10e After the project ends, is there a possibility that the participants will be contacted to participate in any future research (including research conducted on other topics by other research teams) because of their participation in this study? No

#### 19. Recruitment Procedures

- 20. \* 6.11 Will you be recruiting participants for this population on this study? Yes No
  - \* 6.11a Please describe the step-by-step recruitment procedures for this study population. Provide details: who, what, where, when, and how.

All recruitment activities will be conducted by staff at Makerere University School of Public Health and Mildmay who are part of the study team.

Aim 1: We will recruit 40 fisherfolk aged 18 and older who are HIV-negative to participate in the Aim 1 qualitative interviews. Participants will be purposively recruited by gender and occupation [fishermen, other fishing industry workers (e.g., fish cleaners, fish sellers, boat off loaders), CSWs, unemployed]. Participants will be recruited through healthcare providers (e.g., at testing events or healthcare facilities), who will refer to study staff (an interviewer from Makerere University School of Public Health) clients who are HIV-negative. The interviewer who will be present at the healthcare facility or testing event, and will explain the study further. Individuals can participate immediately after post-test counseling, or can schedule a later time for the interview.

Aim 2: Mildmay currently conducts monthly healthcare outreach events (with HIV testing and ART provision, as well as provision of other medical services) at the Nakiwogo and Kigungu landing sites (lakeside locations used by fisherfolk to launch boats), Wakiso District, Lake Victoria. Outreach events are provided in healthcare facilities or in temporary and other structures in the community. During these events, Mildmay staff, Village Health Teams (VHTs), and Beach Management (BMU) leaders conduct community mobilization with fisherfolk prior to these events (e.g., home visits, radio ads) as well as during events (e.g., using bullhorns). As part of this study, Mildmay staff will offer PrEP to 100 eligible HIV-negative fisherfolk who are tested at Nakiwogo and Kigungu landing sites (the first 50 per site). To assess acceptability of PrEP among fisherfolk, after PrEP is offered to HIV-negative testing clients, HIV testing staff will record whether the client agrees or refuses PrEP, and why, and then refer the client to a study interviewer, who will be present at the facility or the event, or who will follow up by phone with interested potential participants for interviews. The interviewer will accompany the client to a nearby private space for study activities (e.g., in a school or church, or outside away from others)

for informed consent and interviewing.

We will interview 20 PrEP-eligible HIV testing clients who refused PrEP and 20 PrEP-eligible HIV testing clients who accepted PrEP at baseline, within a month after HIV testing, to explore barriers to and facilitators of PrEP uptake, with half of clients recruited from each community (Kigungu, Nakiwogo).

We will also interview 40 clients (approximately 20 men, 20 women, approximately half currently taking PrEP and half who discontinued PrEP; approximately half from each community within each category) about 6 months after their PrEP initiation, to explore barriers to adherence, any reasons for discontinuation, and general acceptability of PrEP and the PrEP behavioral interventions, as well as any gender differences. For these 6-month interviews, fisherfolk participants who have initiated PrEP in the last 6 months (during the study intervention period) in one of the study communities will be recruited by the healthcare provider team during check-in calls or other contacts (e.g., during healthcare outreach events, when they receive a PrEP refill) and referred to the study interviewer, who will be present at the facility or the event, or who will follow up by phone with interested potential participants. Interviews will be conducted in-person if possible, or by phone if the participant has traveled far from the landing site or for precautionary measures due to COVID-19.

\* 6.11b Do you have recruitment materials (e.g. advertisements, flyers, letters of introduction, email invitations, and reminders) in draft or final form ready to upload? No

## **Sensitive Information**

- 21. \* 6.12 Please indicate which of the following types of sensitive information will be intentionally accessed, acquired or recorded for any study population as part of data collection. These types of information are legally protected, potentially distressing, or otherwise sensitive. The information can also be considered sensitive because of the subject populations or the context of the study.
  - B. Physical health including diagnosis, treatment, or other private physical health information

22.

23.

2024-N0127

View: RAND SF: Part 7

Part 7: Study documents

#### Introduction

In this section, please upload the study documents (in draft or final form) that are ready for HSPC review

and approval at this time. Please clearly label each document so the materials can be linked to the population-procedures matrix. Include the name of the study population-procedure, and any other pertinent details (such as study phase, wave, etc.) in the header of each consent document and/or file name so reviewers can link the materials to the research procedures-population matrix you completed in Part 4.

Component #	Population	Procedure
9	Adherence supporters of HIV-negative fisherfolk	Intervention (social behavioral component)
6	Adherence supporters of HIV-negative fisherfolk	Semi-structured interviews (Aim 2)
15	HIV-negative fisherfolk	Intervention (clinical component)
14	HIV-negative fisherfolk	Intervention (social behavioral component)
13	HIV-negative fisherfolk	Medical Records
12	HIV-negative fisherfolk	Semi-structured interviews (Aim 1)
11	HIV-negative fisherfolk	Semi-structured interviews (Aim 2)
2	Stakeholders (healthcare providers, community leaders, Ministry of Health policymakers)	Semi-structured interviews (Aim 1)
1	Stakeholders (healthcare providers, community leaders, Ministry of Health policymakers)	Semi-structured interviews (Aim 2)
2024-N02 View: RA	127 AND SF: Part 8	

#### **Part 8: Conclusion**

1. \* 8.1 Does the proposed study involve any ethical issues not already discussed in the study application?

Yes No

2. 8.2 Please enter any other comments or information that you would like to share with the HSPC reviewer that would be relevant to the review.

It should be clarified that the intervention test is of the different implementation modes of PrEP provision (a behavioral intervention), rather than testing the effectiveness of PrEP (a biomedical intervention). This application notes the risks of PrEP (e.g., side effects) as part of the

intervention, although such risks are not expected to be related to the behavioral intervention.

## **Statistical Analysis Plan**

Analyses will compare data from before the intervention to during the intervention period. Separate logistic regression models will be used to predict the likelihood of PrEP persistence (i.e., PrEP possession at 6-months and PrEP possession ratio of >80% in 6-months) with a time indicator (before vs. during the intervention). PrEP user age and gender will be included as covariates. If PrEP persistence is 0% at follow-up, logistic regression, which allows cannot be used as the odds ratio would be undefined. Thus, in this case, Fisher's Exact test will be used to evaluate change in the persistence outcome.

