- 2. To conduct a mixed-methods analysis comparing the implementation of community-based vs. healthcare facility-based PrEP provision for fisherfolk communities on Lake Victoria, Uganda. When this study was initially proposed, the intent was to purchase and supply PrEP to study participants as it was not widely used in the country as a whole, or in fishing communities. Since the study was funded, PrEP use has become more widespread in Uganda and is provided by Mildmay Uganda via a Ugandan Ministry of Health program. As a result, the study will no longer purchase and provide PrEP through the grant, and instead will evaluate enhancements (i.e., behavioral interventions) to the standard of care for providing PrEP in Ugandan fishing communities.

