## \* 5.14a Are you using individual-level data?

Yes No

\* 5.14b What information is included in the datasets you will be using (e.g. medical claims data, arrest records, student test scores, etc)?

We will extract from Mildmay clinic testing records the number of clients tested and who screened positive and negative, and negative and PrEP-eligible; and from medical records whether PrEP-eligible clients who were offered PrEP initiated PrEP, reasons for refusal if clients who are offered PrEP decline to start, PrEP start-date, dates and locations of PrEP refills, and any other dates of contacts with the Mildmay team around PrEP (e.g., reminders, intervention sessions). We will also extract all post-PrEP initiation HIV testing results and dates, to assess whether any HIV-negative clients seroconverted. We will extract administrative data, such as attendance at intervention sessions, dates of when clinic staff contact participants to provide reminders, as well as client socio-demographic characteristics. We will also extract a larger overall dataset that contains de-identified patient-level medical records data for the two study communities, which only contains PrEP refill data (dates and refill duration) without any identifiers or any other information such as socio-demographics, so that we can compute the percentage of refills filled in each community 6 months before the intervention start-date, and during and after the 6month intervention (March 2021-Sept 2022). Update: we will extend the data collection to evaluate implementation of the intervention in the comparison site, which is expected to begin in early 2023. Thus, de-identified data will be extracted from medical records until 6 months after the intervention (likely until December 2023). We will request a no-cost extension from NIH to do so (and thus the project will end March 31, 2024).

\* 5.14c Please name the source(s) of this data and include the url (e.g. school district, health plan, specific city or state, etc)
Mildmay Uganda Clinic

\* 5.14d Availability of data. If it falls under more than one of the options, please select Other and describe.

Requires signed Data Use Agreement, Memo of Understanding, or other signed agreement to obtain

- \* 5.14f Are you required to pay for this data? Yes No
- \* 5.14h Will you be matching this data with any other data you plan to obtain? Yes No

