At Nakiwogo, events will be held in a public temporary space (e.g., tent, church) in partnership with Entebbe Hospital, and at Kigungu, Mildmay staff will use space in the nearby public Kigungu Health Center III to test and treat clients during community mobilization events. In Nakiwogo only, we will conduct an enhanced behavioral PrEP intervention to compare to the standard of care in Kigungu. Specifically, in Nakiwogo, we will have a three-pronged intervention: 1) During healthcare outreach events in Nakiwogo, we will conduct PrEP workshops, in which people who want to know more about PrEP can learn basic facts about PrEP and also can be taught skills about how to advocate for PrEP in their community. These PrEP workshops will be conducted by master trainers, who are Mildmay staff who have been trained by the Ugandan Ministry of Health to conduct health workshops and trainings. 2) Check-in Calls: To support PrEP adherence, healthcare workers will call PrEP users regularly (e.g., every 1-2 weeks), to check in about any questions and to remind them of the next date and place to pick up refills. Calls will be more frequent after PrEP initiation, to ask about side effects. 3) To support PrEP adherence, healthcare workers will encourage PrEP users to select an adherence supporter, who is a family member or friend to whom they disclose their PrEP use. The adherence supporter agrees to remind them to adhere to PrEP and get refills. Healthcare workers will ask the PrEP user for the name and contact information, as well as the age and gender, for the adherence supporter, so that the adherence supporter can be contacted to remind them about refills, as well as if the PrEP user does not show up for a refill. All Adherence Supporters will also be invited to the intervention workshop, which is open to all community members. Note that the first intervention component (PrEP workshop) will be adapted from our current work in Uganda on prevention advocacy among people living with HIV (2016-0227; 2021-N0155). The last two intervention components are standard practices for people living with HIV on antiretroviral treatment, and will be adapted for PrEP users; provider guidance for adherence supporters will also be adapted from our current work in Botswana (2019-0253). To train master trainers and healthcare

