providers for the intervention, we have modified Ugandan Ministry of Health PrEP training slides for healthcare providers and counselors, tailoring them based on the Phase 1 formative work and adding issues of importance to fisherfolk communities. We have received permission from the Ugandan Ministry of Health to make these modifications, and we are regularly meeting with the Ugandan Ministry of Health to update them about the study, and to help develop the intervention.

Per their usual Ministry of Health compliant procedures for PrEP, Mildmay healthcare providers will use an assumed consent procedure for providing PrEP. That is, individuals who attend an HIV testing event at which PrEP is being provided are assumed to consent to being prescribed PrEP when appropriate per Uganda Ministry of Health guidelines. Mildmay providers will draw blood to screen for PrEP contraindications [HIV-1 infected or evidence of possible acute HIV infection; allergy to Tenofovir Disoproxil Fumarate (TDF) and/or Emtricitabine (FTC); poor renal function; unwilling/unable to return for 3-monthly HIV testing, counseling and safety monitoring visits; weight <35kg]. Those eligible can obtain PrEP during Mildmay's outreach events, either in a temporary community-based venue at Nakiwogo, at Entebbe Hospital near Nakiwogo, or at Kigungu Health Centre III. Per Ministry of Health guidelines, most fisherfolk are eligible for PrEP as members of a high risk key population (with a high prevalence of multiple partners, transactional sex, alcohol use/abuse, serodiscordant relationships, and inconsistent condom use).

Update: After completion of the intervention in the intervention site, Nakiwogo (in Sept 2022), the implementing partner will provide the intervention to the comparison site, Kigungu. We will continue to collect de-identified PrEP user data to evaluate implementation at the comparison site.

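### The protocol sets Nakiwogo against standard of care in Kigungu, but the SAP models only before versus during, so the between-site difference in persistence is never estimated

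*Combined protocol and SAP*

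**What the plan says.** Item 5.10a states the design: "In Nakiwogo only, we will conduct an enhanced behavioral PrEP intervention to compare to the standard of care in Kigungu". Its later update says that, once Nakiwogo has finished in September 2022, "the implementing partner will provide the intervention to the comparison site, Kigungu". Under Specific Aim 2 (item 3.2) the study "will evaluate enhancements (i.e., behavioral interventions) to the standard of care for providing PrEP in Ugandan fishing communities".

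The Statistical Analysis Plan is one paragraph. It fits separate logistic regressions for two outcomes, PrEP possession at 6 months and a possession ratio above 80% over 6 months. Each model is fitted "with a time indicator (before vs. during the intervention"), with age and gender as covariates. If persistence at follow-up is 0%, Fisher's exact test of the same change over time replaces the regression. Neither community is named.

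Item 5.14b describes two kinds of data. One is clinic and medical records, with PrEP start and refill dates "as well as client socio-demographic characteristics". The other is a larger de-identified refill dataset for both communities, with refill dates and durations but no socio-demographics, meant to "compute the percentage of refills filled in each community 6 months before the intervention start-date", and during and after it. Data collection was then extended to "evaluate implementation of the intervention in the comparison site, which is expected to begin in early 2023".

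**The concern.** The comparison that item 5.10a gives as the reason for confining the package to one site has no counterpart in the SAP. A before/during indicator measures change over time. Community mobilisation and PrEP messages drawn from the formative work are described for both landing sites (item 5.10a), and item 3.2 says that PrEP has become more widespread in Uganda. Influences of that kind could move persistence at both sites, although the documents report no such drift and do not date the messages relative to the before period. Kigungu is the data source that could separate shared change from the package, and the SAP does not say how, or whether, Kigungu enters. At stake is whether a reported change in persistence can be set against standard care.

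**Working it through.** **The text, reading by reading.** The SAP has no figure to reproduce: no alpha, power, effect size, rates or sample-size calculation. The word separate refers to the two outcomes, not to sites. Three readings are possible.

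- *Nakiwogo only.* An uncontrolled before/after estimate. Any change shared with Kigungu is part of it.
- *Both sites pooled.* Treated and untreated users share one time effect. Shared change is still included, and a real Nakiwogo effect is diluted.
- *Each site separately.* Two time effects. Kigungu's roll-out comes later, so a one-off shock around Nakiwogo's start need not recur in Kigungu's own contrast. A steady trend would bias both, and the difference in change is not estimated.

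The Fisher fallback also looks only at change over time, so it behaves like the main model.

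**Illustrations.** All rates are assumed: equal n per site-period, two-sided 5%. The value n = 50 is borrowed from the recruitment text, "landing sites (the first 50 per site"), but that number counts PrEP offers, not analysed users, so n = 100 is shown as well.

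*Shared drift, no intervention effect.* The before/during columns come from exact enumeration of two binomials. The interaction column is simulated, with the same drift at both sites. Each cell gives Wald / likelihood ratio.

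| Drift | n per cell | Nakiwogo before/during rejects | Site-by-period rejects |
|---|---|---|---|
| 10% to 15% | 50 | 7.8% / 12.8% | 3.5% / 5.7% |
| 10% to 15% | 100 | 16.8% / 18.9% | 4.2% / 5.4% |
| 10% to 20% | 50 | 24.0% / 30.4% | 3.5% / 5.6% |
| 10% to 20% | 100 | 49.1% / 51.8% | 4.4% / 5.1% |
| 20% to 30% | 50 | 19.7% / 21.2% | 4.4% / 5.1% |
| 20% to 30% | 100 | 35.9% / 37.9% | 4.7% / 4.8% |

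*Dilution by pooling.* Nakiwogo goes from 10% to 30% and Kigungu stays at 10%. The Nakiwogo odds ratio is (0.30/0.70)/(0.10/0.90) = 3.86. The pooled during-rate is (0.30 + 0.10)/2 = 0.20, so the pooled odds ratio is (0.20/0.80)/(0.10/0.90) = 2.25.

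*Zero persistence.* If both sites fall from 8/50 to 0/50, Fisher's test within Nakiwogo gives p = 0.006. The between-site difference in change is 0.00 by construction, with a Wilson-based 95% interval of -0.16 to 0.16. This shows only that the fallback cannot supply the contrast.

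*Precision of the interaction.* The variance of a log-odds is 1/[n p(1 - p)]. For 10% to 30% against a flat 10%:

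- Single site: 1/0.09 + 1/0.21 = 11.11 + 4.76 = 15.87, divided by n.
- Interaction: 15.87 + 2(11.11) = 38.10, divided by n.
- Standard-error ratio: √(38.10/15.87) = 1.549. With 10% to 20% at both sites it is √2 = 1.414.
- Log odds ratio: ln 3.86 = 1.35. Power is approximately Φ(1.35/SE - 1.96). At n = 50 this is 67% for the single site and 34% for the interaction. At n = 100 it is 92% and 59%.
- n per cell for 80% power: (1.96 + 0.84)² × 15.87/1.35² gives 69 after rounding up; with 38.10 in place of 15.87 it gives 165.

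**The case against.** Item 5.10a says only that the two sites are to be compared. It names no outcome and promises no hypothesis test. Aim 2 is a mixed-methods analysis, and the plan also has refill percentages by community and interviews divided between the communities. With one community per condition, an interaction cannot separate the package from a shock specific to one site, and variation between communities cannot be estimated. A within-site before/during analysis is a legitimate pilot result if it is described as such.

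Most of this stands. It means the remedy is an estimate with stated limits, and that aligning the claims with the model is an acceptable alternative. It does not remove the mismatch: the refill percentages have no inferential analysis attached, the interviews are qualitative, and no planned model quantifies the difference between sites in persistence.

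Three stronger readings are tempting and are not supported. A reader might infer that shared change would be mistaken for an intervention effect however the model is fitted; the per-site reading with a later Kigungu roll-out gives partial protection. A reader might infer from the rejection rates that the planned test is badly inflated; those rates rest on assumed drifts, and at 10% to 15% with n = 50 rejection is only 8% to 13%. A reader might infer that age and gender adjustment is impossible because the community-wide refill dataset lacks both; the SAP names no dataset, and the clinic records include socio-demographics, so no conflict is shown.

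**Conclusion.** The concern holds as a mismatch between the design in item 5.10a and the SAP: the comparison of Nakiwogo with standard care in Kigungu is not estimated on any of the three readings. In Nakiwogo alone or pooled, shared change cannot be distinguished from an intervention effect, and pooling also dilutes a real one. Fitted per site, the analysis is partly protected against a one-off shock but not against a steady trend. The conclusion rests on the text alone. The size of any bias is unknown, and every rate above is an assumption. This should be fixed. It does not make the before/during analysis invalid as a description of within-site change.

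**What to change.** 1. **Name the inputs.** State which sites, users, dataset and calendar periods enter each model. Use the linked clinic records for the age- and gender-adjusted model, or run the interaction unadjusted on the community-wide refill data. The linked records cover those who signed a medical release, and item 5.14b lists refill duration only for the community-wide set, so confirm that the linked records hold it.

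2. **Add site and site-by-period terms for each outcome.** Use the same PrEP-start windows and the same accrual cut-off at both sites, set so that every Kigungu 6-month window closes before Kigungu's roll-out. A September 2022 start reaches 6 months in March 2023, which may fall after an early-2023 roll-out. If roll-out were January 2023 (assumed), starts from July 2022 onward would be cut at both sites; cutting them only in Kigungu would leave cohorts from different calendar periods. Report the interaction with its confidence interval as the estimate for the item 5.10a comparison. Keep the within-Nakiwogo change and the later Kigungu change as separate results.

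3. **Zero persistence.** Pre-specify a method that still gives a between-site contrast, such as penalised logistic regression or a difference-in-differences of proportions with a suitable interval. Keep Fisher's test as a within-site supplement.

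4. **Limits.** State the common-trends assumption on the chosen scale, that site-specific shocks stay confounded with one site per condition, and that the interval reflects within-site sampling only. Restrict causal wording to match. If no between-site contrast is added, limit claims to within-site change.

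The cost is SAP wording and modest extra analysis on data already planned for both communities, some users lost to the shared cut-off, and the loss of precision shown above.
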